Randomization will be stratified at the OHGPS level and by GP's intervention vehicle in blocks of six. Obtaining an informed consent is important because the study focusses on emergencies where extensive explanation of the study is often limited due to time constraints. Outcome data after 30 days will be requested from the regular GP and checked in the emergency department's electronic health record.

Keywords: out-of-hours general practice service, monitoring, emergencies, home visits, parameters, referral, outcome, (informed consent, randomisation).

INTRODUCTION

Calls to an out-of-hours general practitioner's service (OHGPS) for an emergency could originate from different types of callers. Based on the information provided over the phone, it is sometimes difficult to figure out to what extent the call can actually be considered urgent. General practitioners (GP) or their dispatchers frequently must rely on their own gut-feeling [1].

The development of the out-of-hours services by GPs in Belgium recently led to the introduction of a uniform urgent phone number 1733 for out-of-hours calls. The phone operator can send a GP for an urgent home-visit, ask the patient to go to the OHGPS, to wait until the next available appointment with his/her regular GP or go to the emergency department (ED) immediately [2]. To optimise use of medical workforce, a pilot project was set up, combining the above mentioned 1733 number with the 112 national emergency number, the regular emergency dispatch service. The 112 dispatcher can decide (I) to send the MET, (II) a PIT, similar to MET but without a doctor on board, (III) an ambulance, (IV) request the patient to go to the ED, or (V) send a message to the OHGPS dispatcher. The latter can decide upon the most suited approach. Not only the 112 dispatcher, but also the OHGPS phone operator must be able to differentiate an urgent situation from the vast majority of semi-urgent calls.

The assessment of an acutely ill patient relies on the clinical data observed and measured by GPs. For years, GPs measured blood pressure and pulse rate, observed heart rhythm and respiratory sounds. Over the last 50 years, a few additional technological advancements have facilitated early diagnosis: Electrocardiograms (ECG), thermometers and some point of care tests (POCT) such as urine dipsticks or blood glucose measurement. Only recently, POCTs were further introduced after a gap of nearly 30 years [3]. Some devices such as a portable pulse oximeter [4,5,6] and devices to document one-lead ECG recordings [7] were progressively introduced in routine daily care.

During an urgent home visit, a GP is typically multitasking: taking clinical history, performing clinical examination, formulating a diagnostic hypothesis, administering medication and also checking as many vital parameters as possible. There is hardly any time left to make notes. Consequently, GPs might forget to control the evolution over time of some parameters or, if checking parameters too frequently, to monitor the patient appropriately.

Monitoring of parameters by pulse oximetry, is very helpful to alarm the physician whenever something goes wrong. Generally, GPs do not have a monitoring device similar to the one EPs carry. Most research focused on monitoring chronic diseases (e.g. diabetes, renal failure), assessing a patient with pulse oximetry [3,8,9] or event monitoring by a HR monitoring device or one-lead ECG recordings [7,10,11].

Arriving at the scene, the EP requires the history of the event, a read-out of the vital signs and symptoms, and the measured parameters. Communication of these data to the ED staff was examined especially for emergency service personnel (ambulance staff, nurses, EPs). There was a considerable loss of orally transmitted information by transferring the patient to the ED [12,13].

The possibility of checking these records retrospectively, is not only useful to review data during the period between the GP's and the EP's arrival. Data can also be reproduced at a later stage, e.g. during transport of the patient or during stay at the ED. The information of AEDs for instance, used in out-of-hospital cardiac arrest by bystanders, is important to examine the onset and evolution of the cardiac rhythms and bystander basic life support [14]. Also, all information, recorded by a GP before the arrival of the EP, is crucial to support diagnosis, treatment and prognosis.

After an extensive literature review, I did not find a single paper on the use of portable monitoring devices by GPs in out-of-hospital emergencies. There are many devices on the market capable of measuring more than one parameter. Unfortunately, most of them are too large and heavy, and do not record all parameters, are unable to transmit results to another device, or do not contain a reproducible memory.

I found a monitoring device, called PICO™, which is portable, fits in a doctor's bag, and immediately shows all parameters and curves on the display, similar to the EDs' monitors [15]. The data on this device can also be transferred on-site to a computer in which retrospective review of the parameters is possible. All data are saved on both devices. Although this device is not yet commercialised, the future aim is to transfer the data to any device such as a tablet or a smartphone and by all possible means of communication to the prehospital or ED staff.

We aim to investigate if

1. the use of the PICO™ monitoring device could improve GPs' decisions to refer to hospital or not in urgent cases;
2. there is a difference between the diagnosis with and without the use of the monitoring device using the final diagnosis by the electronic health record of the own GP of the patient;
3. the call to send a GP for an emergency contained sufficient information for the OHGPS phone operator to take an appropriate decision;
4. the build-in alarms help the GP during his intervention;
5. the PICO™ is easy to use during an emergency;
6. the use of the device makes them feel more confident in transmitting the information to the MET.

METHOD

Study Design

During this prospective randomized controlled trial, we will include all patients contacting the OHGPS via 112 or 1733 over the phone who are subsequently visited by physicians from OHGPS in Belgium. If recruitment is slower than anticipated, a second OHGPS will be recruited.

Whenever a patient requires medical help, his family or a bystander can call the 112 emergency number or, if a GP is needed, the 1733 number (Figure 1).

The urgent calls received by the OHGPS phone operator are transferred to the GP on duty. For the other calls, the patient is invited to go to the OHGPS. For home visits, GPs have a dedicated car with a chauffeur at their disposal, to avoid parking problems and to have additional support available (Figure 1).

For each home visit, GPs on duty register all visits, urgent and not urgent, as they usual do. Because they have to write a report to the patient's GP, presenting complaint(s) and diagnosis are recorded for every home visit.

Before the study, all GPs and chauffeurs are informed about the study design and the detailed procedures, and have to sign the informed consent form (ICF) respectively for GPs and chauffeurs. The main researcher developed an extensive training video showing how to use the PICO™ monitor. All GPs and chauffeurs of the OHGPS have access to this video at any time and will receive a written manual.

Each patient seen at home is considered as having requested an urgent visit and, consequently, is eligible to enter the study. Before entering the residence, each patient will be allocated to one of two arms, according to the results of the randomisation process [16] (see the procedure in the statistics section). The first arm is the intervention arm where the monitoring device (figure 2) is used, additional to usual care, and the second arm is usual care only, without the use of the monitoring device.

[figure not shown]

Figure 1: flowchart of calls arriving at the emergency dispatch centre in the region of Leuven, Belgium

To be able to include the patient, the GP needs to obtain an ICF from the patient or his legal representative or when the requirements of the WMA Declaration of Helsinki are fulfilled (articles 29 and 30) [17]. The reasons for including a patient if no IC can be obtained and if there is no legal representative present, are: a comatose patient, patients with stroke, patients unable to speak, patients in critical situations in which the GP does not have sufficient time to obtain the informed consent. E.g. acute HF with acute pulmonary oedema, patients with hallucinations or confusion from any kind of origin, patients who give oral informed consent but afterwards suffer of cardiac arrest (resulting in the GP to initiate CPR). In all other cases, when taking an informed consent is deemed not feasible, the reason will be recorded on the patient's ICF.

Once the patient can be included, the GP performs his clinical tasks (examination). The chauffeur applies the PICO™ device (figure 2) according to the randomisation process. He checks if all parameters and curves are correctly recorded. The GP can follow the evolution of these measurements and both the GP and chauffeur will be alarmed if the device records any abnormal parameter result in a patient.

Immediately after the home visit, the GP completes an 'intervention form' as usual, containing the reason of the call, the probable diagnosis, decision and treatment. Additionally, the self-recorded parameters, the use of the monitoring device (yes or no), the level of urgency, the confirmation that an informed consent is obtained, the user-friendliness of the device, its utility and if the use had any influence on their intervention and/or decision, will be recorded. How the communication with the healthcare professionals went will also be recorded.

The objective is also to retrieve the diagnosis of each case 30 days after the intervention, from the patients' regular GP's health record and, if the patient was admitted, from hospital.

The monitoring device

The PICO™ is a stand-alone patient monitor displaying 0-2 curves and/or 0-6 measured or calculated parameters which can be displayed simultaneously while the monitoring function is working. The device can be operated by using its touchscreen and buttons and has a 3-level alarm system that indicates whenever a parameter is out of the set limits [18].

Figure 2: The PICO™ monitoring device. From left to right and from top to bottom: HR, SpO₂, temperature, RR, pulse rate, the blood pressure parameters and one of the vital signs curves, in this case the SpO₂ curve.

The basic functions of the monitor (ECG, respiration, temperature and SpO₂) are preconfigured. However, external measuring modules can be connected. Respiration is measured by measuring impedance (from the ECG electrodes), SpO₂ and pulse rate through a pulse-oximeter and temperature with one channel measurement. The 3-channel ECG displays HR and arrhythmia analysis. Systolic and diastolic parameters of blood pressure can be entered different times manually. With the Bluetooth network connectivity all data can be transferred to a PC or tablet on which a special developed software shows the parameters and curves as on an ED monitoring screen [18].

Inclusion criteria

Registration of the numbers of calls at the 112-1733 dispatch centre and the results of the triage decisions will be done. From the calls sent to the OHGPS dispatch centre I will investigate how many are triaged to either delay of care by referring patients back to their regular GP, invitation to attend the GP's out of hours centre or sending out a GP for an urgent home visit.

All GPs on duty and chauffeurs of the OHGPS in Belgium, present during the study period are recruited after signing an ICF. GPs' age, gender and years of practice will be recorded. (Table 1).

All patients 18 years of age and older, for whom a home visit is requested, seen by a participating GP will be included if the informed consent form is signed either by the patient or by the legal representative, either onsite or at a later time.

Table 1: Demographics of GPs and of patients, distribution of patients (total number of patients seen during study period: N=...)

		GPs		PATIENTS									
				Total number of home visits*		Excluded (N=)				Included urgent visits (N=)			
				N=	%	N=	%	n=	%			n=	%
Gender	M												
	F												
Age	Mean												
	Min												
	Max												
Practice	2 or more GPs												
	Solo												
	GP in training												
Experience	> 25 y												
	6-25 y												
	0-5 y												
Total number of patients managed at OHGPS ***													
								N=	M (n=) (%)	F (n=) (%)			
Care provided at the OHGPS													
Care provided during home visits by OHGPS								d	d D	d d			

* Total number: total number of patients for whom a home visit was requested during the registration period.

** Other reasons: when the GP on-call deems the intervention as not urgent, ICF withdrawn after previous acceptance,

*** Distribution of patients: number of patients cared for onsite in the OHGPS and number of patients for whom a home visit is requested.

Exclusion criteria

Patients younger than 18 years of age, not seen during home visits, failed to provide informed consent, with an acute trauma but not in a possible life-threatening situation (e.g. a broken bone), found lying on the street or seen after the intervention of an ambulance, a PIT or a MET (because in such situation monitoring devices are already on scene before arrival of a GP).

Reasons for exclusion will be recorded (not meeting inclusion criteria, refusing to participate, other reasons): these patients will not be included in the study.

Statistics

Randomisation

The cases are randomly assigned to two arms on a 1:1 ratio (via random number generator on “<http://www.random.org>” [16]): 1 group with and 1 group without the use of the monitoring device PICO™. Randomization will be stratified at the OHGPS level and by GP’s intervention vehicle and will be randomised in blocks of 6.

Sample size

The OHGPS is open on weekends, from Friday 19:00 h until Monday 08:00 h, and the service responds to an average of 54 calls for urgent home visits per week-end. Based on prevalence of emergency

diagnoses in the Intego data [19], I calculated that 10% of the calls are very urgent and 25% require an urgent decision but are not always followed by a hospitalisation. The presumption is that GPs generally refer 21% of the patients inappropriately to hospital or to patient's own GP. To achieve a minimal clinically significant difference of 11% more patients receiving an appropriate decision regarding referral to hospital or not in the intervention group compared to the control group, one will need 866 patients, 433 patients in each arm.

To yield minimally 866 included patients during urgent home visits, the estimation that the study will last for minimum 6 months is based on the consideration that an average of 25% of patients will not provide informed consent.

Data recorded

The aim is to record

- the number of calls at the 112 dispatch centre by means of the 112 or 1733 dial number and the 112's decision.
- the number of calls dispatched from 112 to the OHGPS phone operator.
- the decision of the OHGPS phone operator.
- all data on the intervention form for both study arms, for each patient, who gave IC. These data consist of those filled in by the GP on-call immediately after the intervention (Table 2)
 - o first (when deciding on referral) and final (when completing the intervention form) diagnostic hypothesis;
 - o referral to hospital or not;
 - o parameters and curves inspected and results;
 - o if any alarm was given and noticed;
 - o the impact of the device parameters on the decision;
 - o if the device brought new elements;
 - o the feeling of the GP about the improvement or not by the device in communication with the healthcare professional;
 - o which parameters helped the communication and if they were showed or viewed by the EP.
- After 30 days
 - o the information provided by the patient's own regular GP, regarding the patient's outcome;
 - o the information concerning the diagnosis at arrival at the ED and, if available, the outcome of the patient until day 30 of the hospital admission.

Analysis

I will compare the amount of (verified or experienced) emergencies with the non-urgent home visits, the number of patients correctly referred to hospital or not. The difference in proportions in both groups will be tested by the Z-test. I will also test for the difference in proportions in the groups using the monitoring device and the usual care group, with the z-statistic for two-sample test of proportions reporting the z-test statistic and the associated *p*-values. All *p*-values smaller than 0.05 will be considered statistically significant. The statistical analyses will be performed with R software version 3.5.1 [20].

The definition of an incorrect referral is stated as follows:

- When a patient is referred to hospital and released within 12 hours. However, if the referral is made only for a diagnostic test, e.g. an X-Ray, an ECG, a blood test, advice of a consultant .., and no hospitalisation followed, it is considered as a correct referral.
- If a patient is referred to hospital only for a diagnostic test (e.g. X-Ray) and no hospitalisation is requested, but an in-hospital decision is made to hospitalise the patient.
- If a patient is referred to his own GP but needs a hospitalisation within 48 hours.

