For hospitalised patient the discussion about correct referrals leads to important decisions. The threshold is set at 12 hours. When a patient is referred to hospital for admission and he stays more than 12 hours in hospital (at the ED), it is considered a correct referral. A correct referral is when the patient is referred only for an investigation, e.g. a X-Ray or an ECG or a blood test, and was not hospitalised. If the referral for an investigation leads to admission to hospital, it is considered as an incorrect referral, as well as if a hospitalisation is requested and the patient leaves the hospital within 12 hours.

Parameters and communication

I currently could not find literature concerning the accuracy of the communication between GPs and EPs. However, it is described in the literature that the communication in-between emergency professionals at any level was not optimal and could certainly be improved [12]. They tend to focus on diagnosis and give incomplete information on parameters or signs and symptoms [13,26]. In this trial, the aim is also to assess whether the GPs' communication with the EPs is better when the monitor is used than when it is not used. Moreover, the objective is also to know which of the parameters is used as an additional argument in the communication, either orally, either by showing the parameter(s) on the device, or by recording the parameter(s) in the referral letter.

Comments of the GPs on-call

On the intervention form, GPs are asked to record elements regarding communication, user-friendliness of the device and general comments. All answers will be coded by two investigators separately and, in case of disagreement, after agreement between both or after consulting a third person.

Based on the results, general conclusions can be drawn for improvement of the device and for future research.

Outcome after 30 days

A letter will be sent to the regular GPs of the included patients 30 days after the GP-on-call intervention, to know if the patients stayed at home more than 48 hours and what the evolution was until day 30: cured, relapse, needed hospitalisation after more than 48 hours for the same reason or not, patient was not seen again or was not a patient of the practice. I also will check whether the GP received a discharge letter of the hospitalised patient. That information aims to evaluate the correct or incorrect nature of the referral by the visiting GP on-call.

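### Aim 2 takes its reference diagnosis from a record that the on-call GP reports to, so for patients neither admitted nor seen again the diagnosis is checked against itself or against nothing

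*Combined protocol and SAP*

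**What the plan says.** Aim 2 (Introduction, list of aims) asks whether diagnoses differ with and without the device, "using the final diagnosis by the electronic health record of the own GP of the patient".

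Method, Study Design, describes the diagnosis under test and where it goes. The on-call GP fills in a form right after the visit, "containing the reason of the call, the probable diagnosis, decision and treatment". On the report to the own GP it says: "Because they have to write a report to the patient's GP, presenting complaint(s) and diagnosis are recorded for every home visit". The same section takes the 30-day diagnosis "from the patients' regular GP's health record and, if the patient was admitted, from hospital".

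Discussion, Outcome after 30 days, describes the letter to the regular GP. Its purpose is "to know if the patients stayed at home more than 48 hours and what the evolution was until day 30", and one foreseen reply is "patient was not seen again or was not a patient of the practice". A newly made diagnosis is not among the listed items. For hospitalised patients the section adds the ED diagnosis and follow-up to day 30, and at least two researchers review all the information. Data recorded lists, for the hospital side, "the information concerning the diagnosis at arrival at the ED" and the outcome to day 30 where available.

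The Analysis section compares the reason for encounter with the on-call GP's own first and final hypotheses. It gives no rule for comparing these with the 30-day record.

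**The concern.** A reference diagnosis is useful only if it could have come out differently from the diagnosis it checks. Here the diagnosis under test is sent, for every visit and in both arms, to the keeper of the reference. If the own GP or a hospital assesses the patient afresh, a new diagnosis can confirm or contradict it. If nobody does, there is nothing new to record.

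A carried-over diagnosis agrees with itself whether or not it was right. Measured accuracy would then be too high in both arms, and a real effect of the monitor on diagnosis would look smaller than it is. At analysis, high agreement could not be told apart from simple transfer of the report.

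**Working it through.** **Following the data.** The table shows what reference exists for each kind of patient.

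| Patient after the visit | Diagnosis available as reference |
|---|---|
| Admitted | Hospital diagnosis, with follow-up to day 30 |
| Assessed at the ED, not admitted | ED diagnosis |
| Seen later by own GP | Diagnosis made at that contact, if one is recorded |
| Neither assessed in hospital nor seen again | On-call diagnosis carried over, or none |
| Not a patient of the practice, not assessed in hospital | None from that record |

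The problem lies in the fourth row. No section says which reference applies there, whether these patients are missing for aim 2, or that the own GP's diagnosis must come from a new contact. No masking of the reviewers to arm or to the on-call diagnosis is stated.

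**Size.** The plan gives no agreement rate, target or sample size for aim 2, so there is no figure of its own to reproduce. The following is an illustration on assumed values:

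- true agreement of 70% with usual care and 80% with the device, the same in patients with and without later contact;
- a share u of patients, equal in both arms, whose carried-over diagnosis is scored as agreement.

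Observed agreement = u + (1 − u) × true agreement.
Observed difference = (1 − u) × 10 points.

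- u = 30%: 0.30 + 0.70 × 0.70 = 79%; 0.30 + 0.70 × 0.80 = 86%; difference 7.0 points.
- u = 45%: 0.45 + 0.55 × 0.70 = 83.5%; 0.45 + 0.55 × 0.80 = 89%; difference 5.5 points.
- u = 60%: 0.60 + 0.40 × 0.70 = 88%; 0.60 + 0.40 × 0.80 = 92%; difference 4.0 points.

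The sample needed for fixed power is proportional to [p₀(1 − p₀) + p₁(1 − p₁)] / (p₁ − p₀)².

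- No carry-over: (0.2100 + 0.1600) / 0.10² = 37.0.
- u = 30%: (0.1659 + 0.1204) / 0.07² = 58.4; ratio 1.6.
- u = 45%: (0.1378 + 0.0979) / 0.055² = 77.9; ratio 2.1.
- u = 60%: (0.1056 + 0.0736) / 0.04² = 112.0; ratio 3.0.

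The simpler factor 1/(1 − u)² would give 2.0, 3.3 and 6.2. It is too large because it ignores that the variance falls as agreement approaches 100%.

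With the planned 433 per arm, a number set for the referral outcome and used here only as the patients available, power on the same assumptions is 93% at u = 0, 78% at u = 30% and 61% at u = 50%.

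**The case against.** The strongest reply is that no section says the report's diagnosis is copied into the own GP's record, or that a copied entry would count as that record's final diagnosis. Replies of no further contact are an explicit category, so these patients can be identified and treated as missing. The Analysis section already promises to count missing values, give reasons, compare complete with incomplete cases and consider multiple imputation.

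This stands in part. Self-comparison is a possibility that the plan leaves open, not a stated procedure. But the missing-data text acts on empty fields, and a carried-over diagnosis leaves the field filled. Nothing in the plan links the no-further-contact reply to the reference for aim 2.

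A reader might also infer that the hospital reference is unusable because the ED physician may have the GP's handover. The documents do not support this. Hospital information includes follow-up to day 30 as well as the arrival diagnosis, and knowing a referral diagnosis is not the same as copying it. By that standard the own GP's later diagnosis would fail too.

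A reader might further infer that the bias favours the device, because reports backed by monitor readings would be accepted more readily. The documents mention readings in communication with emergency physicians and in the referral letter. They do not place them in the report to the own GP. If u differs by arm the bias can go either way, and the plan gives no ground for naming a direction.

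**Conclusion.** The point holds for aim 2, and within it for patients who have no new assessment after the visit. For them the on-call diagnosis is either compared with itself or has no reference, and the plan does not say how either case is handled.

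On the assumed 70% versus 80%, with equal u, a true 10-point difference reads as 7.0, 5.5 or 4.0 points at u of 30%, 45% or 60%. These figures rest on assumed agreement rates, on every patient without a new assessment having a carried-over diagnosis, and on an unknown u. If some of these patients have an empty record instead, they are missing and the dilution is smaller.

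It would be going too far to conclude that the trial's main result is compromised. The sample size is set for correct referral, which is defined by length of hospital stay and admission within 48 hours and does not use this reference diagnosis.

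**What to change.** Define the reference for aim 2 as a diagnosis made after the home visit, either by the hospital (ED or discharge, using the follow-up to day 30) or by the own GP at a later contact. Add two items to the 30-day letter: the date of first contact after the visit, and the diagnosis made at that contact.

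Classify each included patient as confirmed, contradicted or not independently verified. Report all three by arm with all included patients as denominator, and do not count unverified patients as agreement. Code reference diagnoses without sight of the arm or the on-call diagnosis.

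The three-way table exposes the unverified cases but does not by itself remove the dilution. At u = 30%, confirmed is 0.70 × 70% = 49% versus 0.70 × 80% = 56%, still 7 points apart. So also report agreement among verified patients: 49/70 = 70% versus 56/70 = 80%. State the caveat that verification may differ by arm, and that patients who return may differ from those who do not.

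The cost is two questions in a letter already planned, some analysis wording, and a coding list without arm or on-call diagnosis. Some patients will openly have no reference, so precision is lower: of 433 per arm, 433 × 0.70 ≈ 303 would be verified at u = 30%, 433 × 0.55 ≈ 238 at 45% and 433 × 0.40 ≈ 173 at 60%. The matching sample multiplier, 1/(1 − u), is 1.4, 1.8 and 2.5. On the same assumptions this is less than the 1.6, 2.1 and 3.0 incurred by counting carried-over diagnoses as agreement.
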